#### 1.0 Research Aims/Objective:

#### 1.1 Research Question(s):

Does Cooled Radiofrequency Ablation (C-RFA) of the articular sensory nerve supply to the knee prior to unilateral total knee replacement result in improved post-operative knee pain scores and decreased perioperative analgesic use as compared to standard perioperative medical therapy?

### 1.2 Null Hypothesis:

Cooled Radiofrequency Ablation (C-RFA) prior to unilateral total knee replacement has no effect on post-operative knee pain scores or pain medication use as compared to standard perioperative medical therapy.

#### 2.0 Research significance:

### 2.1 Background

More than 300,000 total knee joint replacement surgeries are performed per year in the United States and safe, effective management of post-operative pain in these patients, often elderly, deconditioned, obese, or with co-morbid diseases like sleep apnea, can be challenging and often require a multidisciplinary, multimodal approach. Opiates have been a mainstay of

treatment in the post-operative period, although continuous epidurals, peripheral nerve infusions of local anesthetic, intra and periarticular injections have all been used in this patient population with varying degrees of success and complications. Inadequately controlled postoperative pain is not uncommon and can cause multiple untoward effects, including a hyperdynamic circulatory state, increased oxygen consumption, muscle spasm of the quadriceps muscles, increased risk of DVT and increased risk of pulmonary embolism, whereas overmedication with opiates can cause hypoventilation syndrome, sedation, pruritus, constipation, or delirium, especially in the elderly population. Further, poorly controlled pain inhibits early mobilization and hinders post-operative physical therapy, both of which are critical in the early post-operative period to prevent joint adhesions, capsular contraction, muscle atrophy, and delays or limitations in the ultimate functional outcome following TKR.

A new paradigm for treating post-operative pain following TKR may be the use of cooled radiofrequency ablation (C-RFA) of the articular sensory nerve supply of the knee capsule prior to surgery, to desensitize the knee by blocking sensory afferents to the anterior capsule and thereby decrease post-operative pain. The clinical efficacy of radiofrequency neurotomy has been proven in chronic spine pain, cervicogenic headache and trigeminal neuralgia with a strong safety profile in appropriately selected patients. C-RFA is similar in mechanism to conventional RFA: a thermal lesion is created by applying radiofrequency energy through a percutaneous electrode placed at a target neural structure. However, in C-RFA, a constant flow of ambient water is circulated through the electrode via a peristaltic pump, maintaining a lowered tissue temperature by creating a heat sink. By removing heat from tissues immediately adjacent to the electrode tip, a lower but effective lesioning temperature is maintained, resulting in less tissue charring adjacent to the electrode, less tissue impedance and more efficient heating and neurolysis of target tissue. The volume of tissue heated and the resultant thermal lesion size is substantially larger with C-RFA as compared to conventional RFA, conferring a significant therapeutic advantage. Larger thermal lesions increase the probability of successful neurolysis of pain generators that have significant variability in anatomic location.

To date, few publications have demonstrated the use of RFA for knee pain from OA. Choi et al used conventional RFA of the articular nerves in the knee in elderly patients with chronic knee pain from OA in a double blind randomized controlled trial published in 2011. RFA at three nerve locations was performed with image guidance and each lesion was performed at 70 degrees C for 90 seconds with a 22 gauge cannula. Needle placements were at the region connecting the shaft of the femur to the bilateral epicondyles (superior lateral and superior medial genicular nerves) and the shaft of the tibia meeting the medial epicondyle (inferior genicular nerve). Patients who underwent RFA reported at least a 50% decrease in pain scores at one and three months following the procedure, whereas the sham control group had no demonstrable change in pain at these time points. Oxford knee disability scores and patient satisfaction scores were also significantly improved in the RFA group but unchanged in the control group. No adverse events were reported in the 38 patients enrolled in the study. In a single case report, conventional RFA of periarticular nerves in a patient with chronic knee pain following TKR was described with favorable clinical results and drastically improved pain control, but the RFA was performed remote to the time of the TKR for the indication of chronic pain, not to treat perioperativ pain in the immediate postoperative and rehabilitative periods.

Thus, although RFA has been used in patients with chronic knee pain from OA and in one case treating chronic pain many months following knee replacement, C-RFA has not been used in the perioperative management of pain in patients undergoing total knee joint replacement surgery.

The aim of this study is to determine if patients undergoing unilateral total knee replacement obtain any pain relieving benefits from C-RFA of the articular sensory nerve supply prior to surgery, as compared to sham controls who receive only local anesthetic injections of these same nerves without the benefit of ablation treatment.

# 2.2 Significance

If C-RFA of the articular sensory nerve supply of the knee is found to decrease post-operative opiate consumption, provide meaningful pain relief and enhance post op physical therapy, the procedure can be integrated into the TKR perioperative treatment algorithm. Such treatment, if successful, will ultimately improve short and long term pain outcomes, patient satisfaction, and decreased length of hospital stay in a cost effective manner.

## 3.0 Investigational Plan/Protocol Specifics

### General Design and Procedures.

This study design is a *prospective randomized trial* of C-RFA of 3 articular branches of the knee joint versus sham CRFA to examine the effects on post-operative opiate requirements during the first 48 hours after surgery (primary outcome). We will obtain approval from the Institutional Review Board at Northwestern University and will complete an informed consent process before initiating any study procedure.

### Secondary Outcomes include:

- a) Visual Analog Scale for pain: (0 (no pain) to 10 (unbearable pain) scale; at rest, mobilization/ weight bearing.
- b) Knee Society Scale (clinician); WOMAC (patient)
- c) Time to Physical therapy milestones:
  - a. Active SLR
  - b. Time until patient can get out of bed
  - c. Time until patient able to ambulate < 100 feet
  - d. Time until patient able to ambulate around room > 100 feet
  - e. Time until patient is able to climb stairs (quantify specifics, how many steps are considered appropriate?)
- d) Patient Global Perception of Change (GPC)

e) Patient Satisfaction (Likert Scale)

f) Hospital Anxiety and Depression Score (HADS)

- e) SF 12 Questionnaire
- f) McGill Pain Questionnaire
- g) Inpatient length of Stay (LOS; days) and Physical Therapy "clearance for discharge" (days)
- h) Complications of the injection procedure
- i) Medication related adverse effects

A total of 60 patients will be randomized. Participants will complete assessments at these time points:

- 1) Baseline: immediately before the CRFA intervention,
- 2) Immediately prior to surgery (Day of Surgery)
- 3) 48 hours after the surgery procedure
- 4) 1, 3 and 6 months following TKR surgery.

A member of the research team will administer and collect the questionnaires. It will take about 5-10 minutes to complete the questionnaires. The research member will visit the patient at 48 hours to administer the questionnaire and collect data points. It will take approximately 5-10 minutes to complete the questionnaire. In addition, a member of the research team will contact the patient by phone or at scheduled surgical visits at 1 month, 3 months and 6 months.

A member of the research team will look in POWERCHART for physical therapy milestones. Other data points such as medication use, length of stay, time for PT clearance, surgical duration will be recorded. Data collection will be placed on a excel sheet and stored in a pass word protected computer in the department of anesthesiology. Paper data sheets will be placed in a binder and stored in a locked filing cabinet in a locked office located in the department of anesthesiology.

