#### Participants

Inclusion criteria include:

- 1) Adults 30 to 80 years old
- 2) OA of the knee scheduled to undergo their first unilateral knee joint replacement
- 3) Willingness to undergo fluoroscopy-guided C-RFA or sham treatment.

Exclusion criteria include:

- 1) Conditions that preclude C-RFA or sham intervention (e.g. pregnancy, severe cardiac/pulmonary compromise; acute illness/infection; coagulopathy or bleeding disorder; allergic reactions/contraindications to a local anesthetic).
- 2) Prior TKR on either knee
- 3) Inability to write, speak or read in English
- 4) Patient refusal

Recruitment

Site(s) where study will be performed: Department of Anesthesiology, [name] Department of Orthopedic Surgery, [name] Patients who schedule a primary unilateral TKR with their orthopedic surgeon at NM will be asked to participate in the study by authorized research personnel. They will be screened to determine candidacy for the study; if they meet eligibility criteria, they will read and sign an informed consent form to participate. Each participant will be scheduled to see [name] in the Pain Medicine Center for the intervention procedure. They will be asked to be NPO for this visit and arrange a driver to accompany them home. This procedure will be performed 2-4 weeks prior to their planned knee surgery. The research assistant will calculate Morphine Equivalents (ME) of all analgesic medications including opiates, anti-inflammatories and membrane stabilizers.

Each participant will complete the following written outcome measures prior to the intervention: It will take approximately 10 minutes to complete the questionnaires.\* VAS pain score WOMAC questionnaire SF12 questionnaire Hospital Anxiety and Depression Inventory questionnaire McGill Questionnaire

Following the intervention procedure the following data points will be recorded: VAS pain score PGIC Questionnaire Patient satisfaction

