### Risks/Benefits:

The risks of C-RFA of the articular sensory branches of the knee are minimal. Sensory and motor testing of the target structure prior to lesioning reduces the risk of any neurologic injury and the motor nerves are not located at the planned lesion sites. Bleeding or infection can occur with any needle intervention.

Summary of Recruitment:

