### 4.0 Data Analysis:

Primary outcome:

• Between-group difference in analgesic use (MQS III score) at 48 hours.

Secondary outcomes: Between groups at 48 hours, 1, 3, 6 months in:

- 1. Visual Analog Scale for pain (at rest, with mobilization or weight bearing)
- 2. Knee Society Scale (clinician); WOMAC (patient)
- 4. Physical therapy milestones
  - a. Time to active SLR
  - b. Time until patient can get out of bed
  - c. Time until patient able to ambulate < 100 feet
  - d. Time until patient able to ambulate around room > 100 feet

e. Time until patient is able to climb stairs (quantify specifics, how many steps are considered appropriate?)

- 5. Patient Global Perception of Change (GPC)
- 6. Patient Satisfaction (Likert scale)
- 6. Hospital Anxiety and Depression Score (HADI)
- 7. SF12
- 8. McGill Pain Questionnaire

9. Inpatient length of Stay (LOS; days) and Physical Therapy "clearance for discharge" (days)

- 10. Complications of the injection procedure
- 11. Medication related adverse events (i.e. sedation, nausea, pruritus, delirium)

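### Surgical-site events after knee replacement are not a listed outcome and are compared by arm only if someone attributes them to the injection

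*Combined protocol and SAP*

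**What the plan says.** All references are to the combined protocol and SAP.

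- **Safety outcomes.** The secondary outcome list in section 3.0 has two safety items, h and i: "Complications of the injection procedure" and "Medication related adverse effects". Section 4.0 repeats them as items 10 and 11, the second as "Medication related adverse events (i.e. sedation, nausea, pruritus, delirium"), all of them drug effects. Neither place defines an injection complication or gives it a time window.
- **Comparison.** Section 4.0 introduces its list with "Secondary outcomes: Between groups at 48 hours, 1, 3, 6 months in", so the two listed items are to be compared by arm.
- **Timing.** Under Participants: "This procedure will be performed 2-4 weeks prior to their planned knee surgery".
- **What differs by arm.** The active arm has three genicular targets lesioned with heat. The sham arm has needles and local anesthetic without radiofrequency energy (Randomization and Masking; Intervention Procedure Description).
- **Novelty.** Section 2.1 says that "C-RFA has not been used in the perioperative management of pain in patients undergoing total knee joint replacement surgery".
- **Named risks.** Risks/Benefits says: "Bleeding or infection can occur with any needle intervention". It does not discuss the later surgical wound or the implant.
- **Intended use.** Section 2.2 says that if opiate use falls, pain relief is meaningful and physical therapy is helped, "the procedure can be integrated into the TKR perioperative treatment algorithm". It attaches no safety condition.
- **Other fields.** Medication use, length of stay, therapy clearance and surgical duration are recorded. No item on wound, infection, readmission or reoperation appears.

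**The concern.** Randomization varies thermal injury at a knee that is to be operated on within weeks. The new question of harm is whether that injury affects the course of the operation and recovery. The listed safety outcomes sort events by presumed cause, either the injection or a drug. An infection or wound problem that appears after TKR will often be put down to the operation and so fit neither item.

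The surgeons and follow-up staff are blinded, rightly, and cannot tell which knees were ablated. If post-operative events are attributed to surgery in both arms alike, a real excess in the C-RFA arm leaves no trace in the listed outcomes. Counting all such events by randomized arm needs no causal judgement.

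At stake is the basis for the conclusion in section 2.2. The trial could report less opiate use and support adoption without having compared surgical-site events between its arms.

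**Working it through.** **1. The plan's own figure.** The documents give no figure for safety. The only calculation is the primary sample size: 28 per group for a difference of 15 morphine equivalents, SD 19, power .81, two-sided alpha 0.05, Mann-Whitney test. A two-sample t-test needs 26.84 per group. Dividing by the Mann-Whitney efficiency under normality, 3/π = 0.955, gives 26.84 / 0.955 = 28.1. The stated 28 is reproduced, and this point does not rest on any sample-size error.

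**2. Where each kind of event would be counted as the plan stands.**

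| Event | Listed item that covers it | In the by-arm comparison? |
|---|---|---|
| Bleeding or infection at a needle site before surgery | Injection complications | Yes |
| Sedation, nausea, pruritus, delirium | Medication effects | Yes |
| Wound complication, infection or hematoma after TKR | None by name | Only if attributed to the injection |
| Readmission or reoperation of the index knee | None by name | Only if attributed to the injection |
| Surgery postponed or cancelled after the procedure | None by name | Only if attributed to the injection |

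The Knee Society Scale, WOMAC, length of stay and therapy milestones may shift when a serious event occurs, but they do not identify it.

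**3. What all-cause counting could show.** Inputs: 60 randomized 1:1, so n = 60 / 2 = 30 per arm. The documents give no event rates, so the rates below are assumptions shown as a range.

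- *Upper limit with no events.* Solve (1 − p)^30 = α, so p = 1 − α^(1/30). One-sided 95%: 1 − 0.05^(1/30) = 9.5%. Two-sided exact 95%: 1 − 0.025^(1/30) = 11.6%.
- *Chance of at least one event in an arm,* 1 − (1 − p)^30:

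| Assumed true rate | Chance of at least one event |
|---|---|
| 1% | 26% |
| 2% | 45% |
| 5% | 79% |
| 10% | 96% |

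- *Fisher's exact test, 30 v 30.* 5 events v 0 gives p = 0.052; 6 v 0 gives p = 0.024. A split of 6 v 0 is therefore the smallest against an empty arm that reaches .05.
- *Power of that test.* 2% v 10%: 4%. 5% v 20%: 24%. 2% v 20%: 41%.

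The table is worth having for complete capture and a stated limit, not for a hypothesis test.

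**The case against.** The strongest reply is that the plan is less bare than it may look, and that the addition would settle little.

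- **A comparison of complications is planned.** A reader might infer that no safety comparison between arms exists. The heading of the outcome list in section 4.0 contradicts that. The gap is limited to surgical-site events not attributed to the injection.
- **The injection item is undefined and could absorb some of these events.** A reader might infer that surgical complications are certain to go uncounted. The documents do not support that: nothing bars staff from entering an infected knee there, and the outcome list and the list of recorded fields are not expressly closed. What can be said is that such events may be missed and that their capture depends on attribution.
- **The mechanism is not described.** A reader might infer that the lesions lie in the operative field, or that wound harm is the chief new risk. The documents do not describe the incision, its relation to the three targets, or healing after ablation. The argument needs only what they do say: a new combination, heat in one arm, and surgery on the same knee weeks later.
- **The risk statement is general.** It speaks of any needle procedure. The sham arm also has needles at all three targets, so the sentence does not concede a risk that differs by arm.
- **Some pages were not available.** Adverse-event reporting may be described there, so it cannot be said that none exists. The outcome and analysis lists are available, however, and they fix what is compared.
- **The trial is small.** This stands. Thirty per arm cannot rule out modest differences, and the primary analysis is unaffected.

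These replies narrow the point. None of them places surgical-site events, counted whatever their cause, in the planned comparison.

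**Conclusion.** The point holds as a gap in outcome definition. Injection complications and medication effects are compared by arm to 6 months. Surgical-site events after TKR are not listed and enter only through an attribution made by blinded staff. An excess in the C-RFA arm may be missed, while section 2.2 ties adoption to opiate, pain and therapy results only.

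The change is recommended because it is cheap and bears on the trial's intended conclusion; it does not alter the primary outcome or the sample size. Its reach is limited: with no events in 30, rates up to 9.5% (one-sided) or 11.6% (two-sided) stay compatible with the data, and 6 events v 0 would be needed for p ≤ .05.

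The verdict assumes that all 30 patients per arm are followed for these events and that the two outcome lists are the full set of planned safety comparisons. All event rates used above are illustrative.

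**What to change.** Add one item to the secondary outcomes in section 3.0 and the same item to section 4.0:

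*All wound and surgical-site complications, infection, hematoma, readmission and reoperation of the index knee, and postponed or cancelled surgery, from the ablation or sham procedure to 6 months after TKR, counted in all randomized patients regardless of attributed cause.*

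- **Collection.** Use blinded review of the chart that is already consulted for therapy milestones, plus a direct question at the planned 48-hour and 1-, 3- and 6-month contacts. The question matters because the chart may miss admissions elsewhere. Starting at the procedure captures events before surgery.
- **End date.** State one for patients whose TKR does not take place.
- **Reporting.** Tabulate each event type by randomized arm with exact 95% confidence intervals. Say that the comparison is descriptive and give the limits for 0 of 30 (9.5% one-sided, 11.6% two-sided), so that an empty table is not read as proof of safety.
- **Existing item.** Keep the injection-complication outcome as it is, alongside the new one.

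The cost is a few data fields, one question at existing contacts and one table. The downside is that the table cannot rule out modest differences between arms.

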#### Participants

Inclusion criteria include:

- 1) Adults 30 to 80 years old
- 2) OA of the knee scheduled to undergo their first unilateral knee joint replacement
- 3) Willingness to undergo fluoroscopy-guided C-RFA or sham treatment.

Exclusion criteria include:

- 1) Conditions that preclude C-RFA or sham intervention (e.g. pregnancy, severe cardiac/pulmonary compromise; acute illness/infection; coagulopathy or bleeding disorder; allergic reactions/contraindications to a local anesthetic).
- 2) Prior TKR on either knee
- 3) Inability to write, speak or read in English
- 4) Patient refusal

Recruitment

Site(s) where study will be performed: Department of Anesthesiology, [name] Department of Orthopedic Surgery, [name] Patients who schedule a primary unilateral TKR with their orthopedic surgeon at NM will be asked to participate in the study by authorized research personnel. They will be screened to determine candidacy for the study; if they meet eligibility criteria, they will read and sign an informed consent form to participate. Each participant will be scheduled to see [name] in the Pain Medicine Center for the intervention procedure. They will be asked to be NPO for this visit and arrange a driver to accompany them home. This procedure will be performed 2-4 weeks prior to their planned knee surgery. The research assistant will calculate Morphine Equivalents (ME) of all analgesic medications including opiates, anti-inflammatories and membrane stabilizers.

Each participant will complete the following written outcome measures prior to the intervention: It will take approximately 10 minutes to complete the questionnaires.\* VAS pain score WOMAC questionnaire SF12 questionnaire Hospital Anxiety and Depression Inventory questionnaire McGill Questionnaire

Following the intervention procedure the following data points will be recorded: VAS pain score PGIC Questionnaire Patient satisfaction

### Randomization and Masking Procedures (Treatment vs Control; T vs C)

A computer-generated 1:1 block randomization scheme will be used to assign participants to receive either a CRFA *or* a sham procedure (wherein no RF energy is delivered after needle placement, and only local anesthetic is delivered). Randomization will be performed by the proceduralist immediately before the injection procedure by opening an opaque envelope to reveal the participant number and group assignment printed on an index card. Participants, surgeons and all other study personnel, including those who will perform follow-up evaluations, will be blinded to group assignment. One board certified, fellowship trained anesthesiologist ([name]) with 16 years of injection experience will perform all injections. [name] will not be involved in the collection of any primary or secondary data outcome.

